8.0 SAFETY ANALYSES

The summary of SAEs will be limited to treatment emergent SAEs, which are defined as any serious adverse event with onset on or after the initiation of treatment or any adverse event already present that worsens in intensity following exposure to study treatment.

For each treatment group (control patients, pooled SB623 patients, and each SB623 dose group) and each category of each genotyping subgroup variable, the following results will be presented: number and percentage of subjects with at least one SAE and descriptive statistics for the number of SAEs per patient. For each category of each genotyping subgroup variable, a two-sided Fisher's Exact Test will be used to test for a difference between treatments (pooled SB623 versus control) in the proportion of patients with at least one SAE. For each treatment group, a two-sided Fisher's Exact Test will be used to test for a difference among categories of the subgroup variables in the proportion of patients with at least one SAE.

For each genotyping subgroup variable, a logistic regression analysis of SAE incidence will be performed. The model will include terms for the genotyping subgroup variable, treatment (pooled SB623 or control), and the genotyping subgroup variable by treatment interaction. The p-value for each term in the model will be presented. A statistically significant interaction term would indicate that the effect of treatment on SAE occurrence is different among the categories of the genotyping subgroup variable.

For each genotyping subgroup variable, a dose response analysis of the incidence of SAEs will be performed using a logistic regression model with terms for the genotyping subgroup variable, SB623 dose (as a continuous variable), and the genotyping subgroup variable by SB623 dose interaction. The control group will be excluded from these analyses. The p-value for each term in the model will be presented. A statistically significant interaction term would indicate that the effect of dose on SAE occurrence is different among the categories of the genotyping subgroup variable.

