16.0 ADVERSE EVENTS

16.1 General Information

An **adverse event** (AE) is any untoward medical occurrence in a patient or clinical investigation subject enrolled in the study and that does not necessarily have a causal relationship with the study product or surgical procedure. An AE can therefore be any unfavorable and unintended sign, symptom, or disease temporally associated with the use of the study product or surgical procedure, whether or not considered related to the study product or surgical procedure. This includes any side effects, injury, toxicity, or sensitivity reaction, and may include a single symptom or sign, a set of related symptoms or signs, or a disease. An adverse event is also any laboratory abnormality judged to be clinically significant by the Investigator or Sub-investigator(s) that worsened compared to baseline.

Throughout the course of the study, every effort should be made to remain alert to possible adverse experiences. Patients should be encouraged to report adverse events spontaneously or in response to general, non-directed questioning.

With the occurrence of an adverse event, the primary concern is the safety of the patient. If necessary, appropriate medical intervention should be provided.

An AE **does not** include:

• Medical or surgical procedures (*e.g.*, surgery, endoscopy, tooth extraction, transfusion); the condition that leads to the procedure is an adverse event

Confidential and Proprietary

- Pre-existing diseases or conditions present or detected at the start of the study that do not worsen in severity or frequency
- Situations where an untoward medical occurrence has not occurred (*e.g.*, hospitalization for elective surgery, social and/or convenience admissions)
- Overdose of concomitant medication without any signs or symptoms

A Serious Adverse Event (SAE) is any adverse event that results in any of the following:

- death,
- life-threatening event,
- inpatient hospitalization or prolongation of hospitalization,
- a persistent or significant disability/incapacity or substantial disruption of the ability to conduct normal life functions,
- congenital anomaly/birth defect, or
- an event that may require intervention to prevent any one of the other outcomes listed above (based on medical judgment)

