16.2 Adverse Event Reporting Period

The adverse event reporting period for this trial begins upon Enrollment and ends 12 months after the administration of SB623.

All AEs (both serious and non-serious) and PTCs must be followed until resolution or until a stable clinical endpoint is reached. All measures required for AE management and the ultimate outcome of the AE must be recorded in the source document and reported to the Sponsor.

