12.0 SAFETY ANALYSES

12.1 Adverse Events

All safety analyses will be performed on the safety population.

The summary of AEs will be limited to treatment emergent AEs, which are defined as any adverse event with onset on or after the initiation of treatment or any adverse event already present that worsens in intensity following exposure to study treatment.

The number and percentage of subjects with at least one adverse event, at least one serious adverse event (SAE), and at least one adverse event that led to discontinuation from the study will be presented. The number and percentage of subjects having an adverse event in each System Organ Class (SOC) and having each individual type of adverse event (Preferred Term) will be presented. Fisher's Exact Test will be used to test for differences between treatments (pooled SB623 vs. sham surgery) in the proportion of subjects experiencing AEs in each SOC. This analysis will also be performed for SAEs, except that no statistical testing will be performed. Adverse events will also be summarized at the event level by SOC/Preferred Term and severity, by SOC/Preferred Term and relationship to study product, by SOC/Preferred Term and relationship to surgery, and by SOC/Preferred Term and action taken.

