4.2 Safety Endpoints

The safety endpoints of interest in this SAP are the presence of serious adverse events (SAEs) and the number of SAEs per patient.

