9.0 SAFETY ANALYSES

The summary of AEs will be limited to treatment emergent SAEs, which are defined as any serious adverse event with onset on or after the initiation of treatment or any serious adverse event already present that worsens in intensity following exposure to study treatment.

For each treatment group (control patients, pooled SB623 patients, and each SB623 dose group) and each category of each antibody subgroup variable, the following results will be presented: number and percentage of subjects with at least one SAE and descriptive statistics for the number of SAEs per patient. For each category of each antibody subgroup variable, a two-sided Fisher's Exact Test will be used to test for a difference between treatments (pooled SB623 versus control) in the proportion of patients with at least one SAE. For each treatment group, a two-sided Fisher's Exact Test will also be used to test for a difference between categories of the subgroup variables in the proportion of patients with at least one SAE.

For each antibody subgroup variable, a logistic regression analysis of SAE incidence will be performed. The model will include terms for the antibody subgroup variable, treatment (pooled SB623 or control), and the antibody subgroup variable by treatment interaction. The p-value for each term in the model will be presented. A statistically significant interaction term would indicate that the effect of treatment on SAE occurrence is different between the two categories of the antibody subgroup variable.

For each antibody subgroup variable, a dose response analysis of the incidence of SAEs will be performed using a logistic regression model with terms for the antibody subgroup variable, SB623 dose (as a continuous variable), and the antibody subgroup variable by SB623 dose interaction. The control group will be excluded from these analyses. The p-value for each term in the model will be presented. A statistically significant interaction term would indicate that the effect of dose on SAE occurrence is different between the two categories of the antibody subgroup variable.

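### The genotyping SAP's definition of a treatment-emergent SAE omits seriousness from its second part, so worsened non-serious events can be counted as SAEs (minor)

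*SAP*

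**What the plan says.** Appendix C of the SAP declares its safety endpoints in 4.2 as "the presence of serious adverse events (SAEs) and the number of SAEs per patient". Appendix D declares the same endpoints in its 4.3.

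Appendix C 8.0 then sets the counting rule. "The summary of SAEs will be limited to treatment emergent SAEs". An event qualifies if it is "any serious adverse event with onset on or after the initiation of treatment or any adverse event already present that worsens in intensity", with the worsening dated after treatment. Appendix D 9.0 has the corresponding sentence, but its second part reads "any serious adverse event already present that worsens in intensity following exposure to study treatment".

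The main SAP, 12.1, defines treatment-emergent adverse events of every kind, serious or not. Its second part is "any adverse event already present that worsens in intensity following exposure to study treatment", which is the wording that appears in Appendix C.

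Protocol 16.1 defines seriousness by outcome: "A Serious Adverse Event (SAE) is any adverse event that results in any of the following", followed by a list that includes death, a threat to life, hospitalization and disability. Worsening intensity is not on that list.

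Appendix C 3.4 reports no changes to the protocol-specified analyses, and no reason is given for a wider SAE definition.

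**The concern.** The definition decides which patients are cases in every safety analysis in Appendix C 8.0:

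- the proportion of patients with at least one SAE and the number of SAEs per patient;
- Fisher's exact tests between treatments within each genotype category, and among categories within each treatment group;
- the treatment-by-genotype model ("a logistic regression analysis of SAE incidence will be performed") and the dose-response logistic model.

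A mild headache noted at the Baseline visit that becomes moderate after surgery meets the second part of the definition without meeting any SAE criterion. The same patient would be a case in the genotype tables and a non-case in the antibody tables, for an endpoint stated in identical words. Version 2.0 of the SAP merges the separate plans into one CSR table set, so a difference of this kind would be visible to a reader of the report.

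**Working it through.** The plan gives no figure for this point, so the main check is a comparison of texts. The arithmetic only shows scale.

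**1. The definitions side by side**

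| Place | Events it defines | New events | Events already present |
|---|---|---|---|
| Main SAP 12.1 | all treatment-emergent AEs | any AE | any AE that worsens |
| Appendix C 8.0 | treatment-emergent SAEs | serious AE | any AE that worsens |
| Appendix D 9.0 | treatment-emergent SAEs | serious AE | serious AE that worsens |

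In Appendix C the new-event column carries the seriousness condition and the pre-existing column does not. The pattern is consistent with the all-AE sentence having been adapted in one half only, although the documents do not say so.

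**2. Can such an event arise?** Yes. Under Protocol 16.2 the AE reporting period "begins upon Enrollment and ends 12 months after the administration of SB623", so it opens before surgery. The schedule of activities first collects AEs at Baseline, Day -14 to -1.

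**3. Direction.** The new-event part captures every new SAE. The pre-existing part captures every worsened event, serious or not. The counted set therefore contains all the true cases plus possible extras, so counts and rates can only rise.

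**4. Scale of one patient.** The planned mITT size is about 52 with 3:1 allocation (Protocol 18.6 and 8.1). It is used here as a stand-in for the Safety population.

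- SB623: 52 × 3/4 = 39; 1/39 = 2.6 points.
- Sham: 52 × 1/4 = 13; 1/13 = 7.7 points.

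Genotype cells are smaller, but the documents give neither genotype frequencies nor cell sizes.

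**5. Illustration with assumed rates.** Let p be the true SAE rate and w the share of patients with a worsened, pre-existing, non-serious AE, taken as independent. The counted rate is 1 − (1 − p)(1 − w), and the share of counted cases with no SAE is (counted − p)/counted.

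| p | w = 5% | w = 10% | w = 20% |
|---|---|---|---|
| 10% | 14.5% (31% not serious) | 19% (47%) | 28% (64%) |
| 20% | 24% (17%) | 28% (29%) | 36% (44%) |

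With w = 0 the counted rate equals p.

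**6. Effect on a test, with assumed counts.** Add k non-serious worsenings to the SB623 arm only and apply the two-sided Fisher test.

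| True SAE counts, SB623 vs sham | k = 0 | k = 2 | k = 4 | k = 8 |
|---|---|---|---|---|
| 6/39 vs 1/13 | 0.66 | 0.42 | 0.25 | 0.08 |
| 6/39 vs 3/13 | 0.67 | 1.00 | 1.00 | 0.51 |

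Rates can only rise, but a between-arm p-value can move either way.

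**7. Would copying Appendix D be enough?** Take a non-serious AE that starts before surgery and becomes serious afterwards. Its onset precedes treatment, so the new-event part misses it. It was not serious while already present, so Appendix D's second part, read literally, misses it too. Inserting the single word would replace a possible overcount with a possible undercount.

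**The case against.** The strongest reply is that the sentence begins from a summary of SAEs, so the set is already restricted to serious events and the definition only adds the treatment-emergent condition. Support for this comes from the endpoint in 4.2, the titles of Appendix C Tables 3.1 and 3.2, and the repeated reference in 8.0 to patients with at least one SAE. A programmer could well filter on the SAE flag first.

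That is a plausible intent, but it does not clear the text. The clause stating what a treatment-emergent SAE is defined as is the operative rule. If a prior filter were understood, the word serious in the first part would be redundant, and Appendix D would not need it twice. Two readings that give different case counts are a defect in an analysis plan.

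The points about scale do stand. The scheduled AE record opens only about two weeks before surgery, and the documents give no count of affected events. The outputs concerned are supplementary tests with no multiplicity adjustment (Appendix C 5.5).

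**Conclusion.** The rule in Appendix C 8.0 is wrong as written, and nothing else in the documents corrects it. Followed literally, its SAE counts, Fisher's tests and logistic models can include worsened, pre-existing, non-serious AEs in addition to true SAEs. One added patient is worth about 2.6 points in SB623 or 7.7 points in sham at the planned numbers. Everything in the working beyond that rests on assumed rates or counts, and the effect is zero if no such event occurred. Severity is minor.

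A reader might infer more than this, and the documents do not support it:

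- *That these analyses no longer measure serious events.* The first part of the definition still captures every new SAE.
- *That the genotype and antibody results could not be reconciled.* Listings 16.2.7.1 (all AEs) and 16.2.7.3 (SAEs) allow a case-by-case check.
- *That the trial's safety or efficacy conclusions are affected.* The main SAE incidence table (14.3.1.3) and the primary analysis do not use this definition.
- *That non-serious events were in fact counted.* The documents do not show how the rule was programmed.

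**What to change.** In Appendix C 8.0, let the second part of the definition read "any adverse event already present that worsens in intensity following exposure to study treatment", followed by a new condition: and meets an SAE criterion after treatment. Cite Protocol 16.1 for the criteria. This covers both a pre-existing SAE that worsens and a non-serious AE that becomes serious.

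Put the identical wording in Appendix D 9.0, and apply it to CSR Tables 14.3.1.10.1 and 14.3.1.10.2, whose titles specify treatment-emergent SAEs. Tables 14.3.1.11.1 and 14.3.1.11.2 carry near-identical titles without that qualifier, and the integrated list does not say which pair serves which appendix. State which definition applies to them.

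The cost is one clause in each of two appendices, one programming condition and a line on the tables. SAP addendum 3.0 records that the interim results have been unblinded, so the change should be dated and explained. The CSR should say which rule was programmed and whether any patient's classification changed.

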| HLA | Human Leukocyte Antigen |
| IND | Investigational New Drug |
| ITT | Intent-to-Treat |
| IXRS | Interactive Web/Voice Response System |
| LOCF | Last-Observation-Carried-Forward |
| LSM | Least-Squares Mean |
| MFI | Mean Fluorescence Intensity |
| mITT | Modified Intent-to-Treat |
| OR | Operating Room |
| PP | Per Protocol |
| PRA | Panel Reactive Antibody |
| SAE | Serious Adverse Event |
| SAP | Statistical Analysis Plan |
| TBI | Traumatic Brain Injury |

1.0 INTRODUCTION

This document details the analysis plan for the analysis of antibody variables for the study entitled “A Double-Blind, Controlled Phase 2 Study of the Safety and Efficacy of Modified Stem Cells (SB623) in Patients with Chronic Motor Deficit from Traumatic Brain Injury (TBI)”. It describes the proposed efficacy and safety analyses, including planned summary tables, by-subject data listings, and figures. This document is a supplement to the main statistical analysis plan (SAP).

2.0 OBJECTIVES

The overall objective of the study is to evaluate the safety and efficacy of SB623 cells stereotactically implanted in the brains of patients with TBI.

The objectives of the antibody statistical analyses are to characterize the immunogenicity of SB623 and to examine the effect of the immunogenicity variables on efficacy and safety.

3.0 STUDY DESIGN

3.1 Overview

This is a double-blind, sham surgery controlled study of stereotactic, intracranial injection of SB623 cells in patients with fixed motor deficits from TBI. The study will be conducted at approximately 30 sites in North America (i.e., United States), Eastern Europe (i.e., Ukraine), and Asia Pacific (i.e., Japan).

Table 1 in the main SAP lists the procedures to be followed throughout the course of the study. Antibody data will be collected at Baseline, and Days 8, 28, 84, 168, and 336.

3.2 Method of Assigning Subjects to Treatment

Two groups, Group 1 and Group 2, will receive SB623 and sham surgery, respectively, in a 3:1 randomization scheme. Group 1 will be further randomized in a 1:1:1 ratio to receive either 2.5 million, 5 million, or 10 million SB623 cells. Randomization will be performed via an interactive web/voice response system (IXRS). For subjects enrolled outside of Japan, the randomization will be stratified by Glasgow Outcome Scale-Extended (GOS-E) score (i.e., scores 3, 4, 5 or 6); for subjects in Japan, the randomization will not be stratified.

3.3 Blinding

This is a double-blind study. The blind will be maintained by strict role definition and procedures as described in the protocol.

3.4 Changes to the Protocol-Specified Analyses

No changes were made to the protocol-specified analyses.

4.0 EFFICACY AND SAFETY ENDPOINTS IN THIS STATISTICAL ANALYSIS PLAN

4.1 Primary Efficacy Endpoint

The primary efficacy endpoint in the study is the change from baseline in the Fugl-Meyer Motor Scale (FMMS) score at Week 24 among all patients.

4.2 Immunogenicity Endpoints

The immunogenicity endpoints of interest in this SAP are the antibody variables, which are as follows: flow PRA class I reaction, percent PRA class I, flow PRA class II reaction, percent PRA class II, high resolution anti-HLA antibodies detected (yes or no), MFI value, virtual T cell interpretation, virtual B cell interpretation, and change in donor-specific antibodies relative to previous sample (visit).

4.3 Safety Endpoints

The safety endpoints of interest in this SAP are the presence of serious adverse events (SAEs) and the number of SAEs per patient.

5.0 STATISTICAL CONSIDERATIONS

5.1 General Methodology

The statistical analysis of the data will be performed using SAS[®] version 9.4 or higher. All statistical tests will be performed at the 0.05 significance level.

The antibody variables will be documented using summary tables and subject data listings. Continuous variables will be summarized using descriptive statistics, specifically the number of observations, mean, median, standard deviation, minimum and maximum. Categorical variables will be summarized by frequencies and percentages. For the most part results will be presented for the four treatment groups separately and the three SB623 dose groups pooled. The three SB623 dose groups will be pooled for all statistical tests comparing SB623 to sham surgery, except where noted otherwise (e.g., dose response analyses).

Data listings will be sorted by treatment group and subject ID. All date fields will be presented in a format of ddmmmyyyy (i.e., 01Jan2018) in the listings.

5.2 Adjustments for Covariates

The primary efficacy endpoint, the change from baseline in the Fugl-Meyer Motor Scale (FMMS) score at Week 24, will be analyzed using an analysis of covariance (ANCOVA) model with adjustment for the baseline FMMS score as a continuous covariate.

5.3 Handling of Dropouts and Missing Data

Every effort will be made to minimize the number of dropouts and to document reasons for dropping out.

For FMMS score, the following imputation rules will be followed for missing individual item data:

- (a) Impute missing individual items at post-baseline visits using the Last-Observation-Carried-Forward (LOCF) method.
- (b) Impute missing individual items at baseline in the following two ways (i. imputed with a score of 0; ii. imputed with the first observed post-baseline value).

If there are no missing individual items for FMMS score at baseline, then the FMMS results will be shown only once, rather than once for each case specified in (b) above.

5.4 Multicenter Study

Approximately 52 subjects will be randomized into the study at approximately thirty (30) sites in North America (i.e., United States), Eastern Europe (i.e., Ukraine), and Asia Pacific (i.e., Japan). A maximum of 12 subjects will be enrolled at each Assessment site, and a maximum of 16 subjects will be enrolled or treated at each Surgery or Comprehensive site, respectively.

5.5 Multiple Comparisons / Multiplicity

Multiplicity considerations will not be taken into consideration in the analyses for this Phase 2 study.

5.6 Examination of Subgroups

The primary analyses of the primary efficacy endpoint will be performed on the following antibody subgroups of interest:

- Patients with pre-existing donor-specific antibodies [defined as having any one of the following a) MFI > 1000 for antibodies against donor HLA; b) virtual T cell positive; c) virtual B cell positive] versus no pre-existing donor-specific antibodies.
- Patients with a significant increase in donor-specific antibodies at any post-baseline visit versus no increase or a non-significant increase at all post-baseline visits
- Patients with either pre-existing donor-specific antibodies or a significant increase in donor-specific antibodies at any post-baseline visit versus those with neither.

While the subgroup categories in the first bullet represent true subgroups, being defined at baseline, the subgroup categories in the second and third bullets are not true subgroup categories.

In addition, the HLA mismatch subgroup (further defined in the TBI-01 genotyping SAP) is utilized in an analysis described in Section 8.0. The HLA mismatch subgroups are as follows:

- High degree of mismatch (8-10 mismatch)
- Moderate degree of mismatch (4-7 mismatches)
- Low degree of mismatches (0-3 mismatches)

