9.9 Visit 8: Follow-Up Period (Week 24, Study Day 168 ± 7)

- Pregnancy test (serum β-hCG) for women of childbearing potential only
- Physical Exam.
- Subject Exercise Diary Review
- Leg Activity Monitor data download (applicable for US and Japan only)
- Vital Signs
- Chest X-ray and ECG
- Hematology
- Serum Chemistry
- INR and APTT
- Blood draw for Serum anti-HLA Antibodies
- Blood draw for PBMC
- Imaging (head MRI)
- Exploratory Imaging (Pre- and post-contrast T1-weighted, dual echo, FLAIR MRI, and Diffusion tensor imaging (DTI) with tractography and Dynamic Susceptibility Contrast (DSC) for perfusion imaging)
- Clinical TBI Evaluations (FMMS; DRS; ARAT; Gait Velocity; NeuroQOL (Upper Extremity Function and Lower Extremity Function)
- Global Rating of Perceived Change: subject and clinician, 7-point Likert scale
- Adverse Events
- Concomitant Medications

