The primary efficacy endpoint will also be analyzed using an analysis of covariance model with the following terms: treatment, the presence of prior (i.e., at baseline) antibodies to donor cell HLA antigens, the interaction between treatment and the presence of prior antibodies to donor cell HLA antigens, the baseline FMMS score, and the GOS-E score at screening to test the null hypothesis that the coefficient of the interaction term equals 0.

The relationship between anti-HLA antibodies and the primary efficacy endpoint will be examined. Descriptive statistics for the primary efficacy endpoint will be presented by treatment group and whether or not the subject experienced an increase of antibodies to donor HLA antigens from baseline to Week 24. A normal approximation test will be used to test the null hypothesis that the differences in means between the pooled SB623 group and the control group are equal for subjects with an increase of antibodies to donor HLA antigens from baseline to Week 24 and those without an increase. Analogous analyses will be performed for whether or not a subject experienced the formation of antibodies post treatment to Week 24 (for subjects with no antibodies at baseline).

The primary efficacy endpoint will be summarized using descriptive statistics for the following subgroups of interest:

- Age at Informed Consent (18-<50 years of age, 50-75 years of age)
- Gender
- GOS-E score at screening (3, 4, 5, or 6)
- Baseline FMMS score (0-50, 51-100)
- Lot (SB623 doses only)
- Percentage cell viability (\leq sample median value, $>$ sample median value)

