7.0 EFFICACY ANALYSES

The primary analyses of the primary efficacy endpoint will be comparisons of the least-squares mean (LSM) change from baseline in the Fugl-Meyer Motor Scale score at Week 24 of SB623 treated subjects (pooling all SB623 doses) to sham surgery control subjects for the antibody subgroup variables defined in Section 5.6. For each antibody subgroup variable, the relationship between the subgroup variable and the primary efficacy endpoint will be examined in the following manner. An analysis of covariance (ANCOVA) will be performed with terms for treatment (pooled SB623 or sham surgery), subgroup, the treatment-by-subgroup interaction, and the baseline Fugl-Meyer Motor Scale score. Within each subgroup category, the LSM and its standard error will be presented for the two treatments, together with a 95% confidence interval for the LSM. The difference in LSMs between treatments and the corresponding 95% confidence interval will also be presented, as well as the p-value for the test of the null hypothesis that the LSMs are equal for the two treatments. In order to examine whether the treatment effect differs for different categories of the subgroup variable, an F-test will be used to test the null hypothesis that the coefficient of the interaction term equals 0. Missing observations will not be imputed.

In addition, the primary efficacy endpoint, the change from baseline in the FMMS score at Week 24 among all patients, will be analyzed to examine dose response for the antibody subgroup variables defined in Section 5.6. As for the primary analysis, an analysis of covariance will be performed. The model will include terms for SB623 dose, subgroup, the SB623 dose-by-subgroup interaction, and the baseline Fugl-Meyer Motor Scale score. Dose will be treated as a continuous variable, and the control treatment will not be included in this analysis. The p-value for the test of the null hypothesis that the coefficient of SB623 dose equals 0 will be presented. In order to examine whether the dose effect differs for different values of the subgroup variable, an F-test will be used to test the null hypothesis that the coefficient of the interaction term equals 0 and the p-value will be presented.

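### Two of the three antibody groupings used to analyse Week 24 FMMS can be decided by the Day 336 sample, which comes after the outcome

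*SAP*

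**What the plan says.** Appendix D 5.6 defines three antibody groupings. The first is fixed at baseline. The second is "Patients with a significant increase in donor-specific antibodies at any post-baseline visit versus no increase or a non-significant increase at all post-baseline visits". The third is "Patients with either pre-existing donor-specific antibodies or a significant increase in donor-specific antibodies at any post-baseline visit versus those with neither". Neither of the last two has an upper time limit. Appendix D 3.1 gives the sampling schedule: "Antibody data will be collected at Baseline, and Days 8, 28, 84, 168, and 336".

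The outcome is "the change from baseline in the Fugl-Meyer Motor Scale (FMMS) score at Week 24 among all patients". Appendix D 7.0 compares the "change from baseline in the Fugl-Meyer Motor Scale score at Week 24 of SB623 treated subjects" "to sham surgery control subjects for the antibody subgroup variables defined in Section 5.6". The model is an ANCOVA with subgroup and treatment-by-subgroup terms. A parallel dose-response ANCOVA has a dose-by-subgroup term. The integrated table list keeps the any-visit rule in the titles of Tables 14.2.24.2 to 14.2.24.4.

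Appendix D 5.6 acknowledges that the second and third groupings are not true subgroups, in contrast to the first, which is set at baseline. It says nothing about samples drawn after Week 24. Main SAP 10.1, by contrast, relates the primary endpoint to "an increase of antibodies to donor HLA antigens from baseline to Week 24", and to new antibody formation up to the same visit.

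**The concern.** Appendix D sets out to learn whether an immune response to the implanted cells changes efficacy. An antibody rise before Week 24 could plausibly bear on Week 24 motor function, but a rise that begins afterwards cannot. Counting it places patients who had shown no significant rise by Week 24 in the increase group. If late conversion is unrelated to Week 24 FMMS, this dilutes any real contrast between the groups. If it is related, the direction of the distortion cannot be predicted.

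Two further effects are conditional. If these tables are run at both the Week 24 interim and the final report, a patient's group can change between them while the Week 24 FMMS value does not. A patient without a Day 336 sample also has one fewer chance to be classed as having an increase.

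**Working it through.** The plan states no figure to reproduce, so the check is one of timing, followed by an illustration of size.

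**Timing**
- Outcome visit: Protocol 9.9, "Follow-Up Period (Week 24, Study Day 168 ± 7" days.
- Last antibody sample: Visit 10, Day 336 ± 14 (Protocol 9.11).
- Nominal gap: 336 − 168 = 168 days = 24 weeks.
- Shortest gap within the windows: (336 − 14) − (168 + 7) = 322 − 175 = 147 days = 21 weeks.
- Longest gap: (336 + 14) − (168 − 7) = 350 − 161 = 189 days = 27 weeks.
- Scheduled post-baseline samples: Days 8, 28, 84, 168 and 336. One of the five comes after the outcome.

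**Could a Day 336 increase be late detection of an earlier rise?** Normally not. Appendix D 4.2 defines the change in donor-specific antibodies against the preceding sample. The protocol schedule has no antibody draw at Visit 9 (Week 36). With complete samples, the Day 336 result is therefore compared with Day 168, the outcome visit itself. The exception is a patient whose Day 168 sample is missing.

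**Who is affected?** In the second grouping, only patients with no significant increase at Days 8 to 168. In the third, only those who also lack pre-existing antibodies.

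**Illustration of size (assumed rates).** Let every patient give all five samples, each with the same independent chance p of a significant increase.
- First increase at Day 336: p(1 − p)^4
- Any increase through Day 336: 1 − (1 − p)^5
- Share of the increase group due to Day 336 alone: the first divided by the second

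The last column applies the first formula to 39 SB623 patients (52 × 3/4).

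| p | First at Day 336 | Any increase | Share | Expected of 39 |
|---|---|---|---|---|
| 0.02 | 0.018 | 0.096 | 19% | 0.7 |
| 0.05 | 0.041 | 0.226 | 18% | 1.6 |
| 0.10 | 0.066 | 0.410 | 16% | 2.6 |
| 0.20 | 0.082 | 0.672 | 12% | 3.2 |

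The share is for the second grouping. In the third it would be smaller, because patients with pre-existing antibodies are already in the combined group.

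**The case against.** There are four arguments on the other side.

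**A Week 24-limited analysis already exists.** Main SAP 10.1 has one, and Table 14.2.4.10 keeps it. This is true, and readers will have it. But it uses any increase rather than a significant one, so it does not replace or correct the Appendix D tables. A reader might infer that the two sections apply the same definition with different end dates. They do not.

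**The SAP already warns about these groupings.** It does, but only because they are post-baseline. Appendix E 5.6 also uses post-treatment groups, yet it sets them at Day 8, before the outcome, and explains why they are of interest. The Appendix D caveat does not cover classification after the outcome.

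**The number affected may be very small.** Protocol 4.2 reports no antibody responses in the earlier stroke study with the same cells, doses and route. That study had 18 patients (Protocol 3.3). If all were tested, the one-sided 95% upper bound is 1 − 0.05^(1/18) ≈ 15%. The population differs and the report covers 6 months, so this is not decisive. It does favour the lower rows of assumed p: cumulative conversion to Week 24 is 7.8% at p = 0.02 and 18.5% at p = 0.05. There the expected count is about one or two SB623 patients, although the share is near its highest.

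**These are supplementary analyses.** They carry no multiplicity adjustment in a Phase 2 trial. This stands, and it limits the importance of the point.

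**Conclusion.** The definition is at fault whatever the conversion rate: two of the three groupings let a sample scheduled 21 to 27 weeks after the outcome decide a patient's group in the model for that outcome. The size is unknown. The 12% to 19% range rests wholly on the equal-chance assumption, and in a trial of about 52 it corresponds to roughly one to three SB623 patients. The correction is worth making, but it does not bear on the trial's main conclusion.

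The documents do not support three stronger readings:
- **That most of the increase group could be late converters.** This needs the single last sample to yield more first conversions than the four earlier ones together. For example, 15% late against 10% early gives 0.15/0.25 = 60%. Nothing in the documents suggests such a pattern.
- **That group membership will differ between interim and final.** Appendix D has no interim section, and main SAP 5.4 does not say that these tables are run then. The effect of a missed Visit 10 is also limited, because the schedule requires withdrawn patients to return for it.
- **That every FMMS display by antibody group should stop at Week 24.** Tables 14.2.25.2 and 14.2.25.3 summarise FMMS over time, and FMMS is collected to Week 48. A blanket cut-off would put late converters in the no-increase group for the Week 48 results.

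**What to change.** - **Week 24 FMMS ANCOVA and dose-response analyses** (Appendix D 5.6 and 7.0; Tables 14.2.24.2 to 14.2.24.4): define the increase as a significant increase at any post-baseline sample up to and including Visit 8 (Week 24). This keeps Appendix D's significance criterion and takes only the time limit from main SAP 10.1.
- **Immunogenicity tables** (14.2.26.x): keep the all-visit definition through Day 336.
- **Over-time FMMS displays** (Tables 14.2.25.2 and 14.2.25.3; Figures 14.2.17.x and 14.2.18.x): state in the title which cut-off is used, and do not use Day 336 samples to group results at or before Week 24.

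The cost is one sentence in the SAP, a filter in the derivation and some title edits, with no new data. The downside is that late converters move to the no-increase group for the Week 24 analyses, so the increase group may be slightly smaller.
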